## Protocol Synopsis

### Significance and rationale

Overweight and obesity are linked to chronic diseases like type 2 diabetes mellitus (T2DM). Weight loss helps prevent and manage T2DM. Traditional group-based behavioral treatment for weight loss includes self-monitoring, physical activity, weight, and regular group meetings. Social support also plays a crucial role in group-based treatment, especially when it combines empathy, social support, and healthy competition.

mHealth delivery offers advantages like cost-effectiveness and scalability. It also allows for integrating novel approaches to sustain motivation and engagement, such as social gaming to reward behaviors like self-monitoring and social support. Gamifying an mHealth behavioral weight loss intervention holds promise for promoting and sustaining social support, but research on its direct effects is limited. Despite commercial health apps using gamified approaches, no adult weight loss interventions have used gamified rewards or points, and no studies have evaluated the impact of reward type on desired outcomes.

### Pilot study main results

To explore gamification's role in promoting social support for weight loss, our team developed a mobile app that rewards social support through social gaming. The Social Pounds Off Digitally study, a three-month randomized weight loss intervention, delivered remote content via twice-weekly podcasts. Experimental group participants ( $n=26$ ) lost more weight (-5.3 kg) than the standard app group ( $n=25$ ; -2.2 kg;  $p=0.02$ ). Total points earned predicted % weight loss ( $p=0.01$ ). This diverse study sample (39% African American) represents one of the more inclusive digital weight loss intervention studies

### Study aims

The goal of the present study is to examine the mLife intervention in a long-term study and to isolate the use of points to gamify the intervention in order to ensure that use of social gaming leads to improvements in social support and continued weight loss.

#### Primary aims:

**Aim 1:** Determine if the mLife app plus points intervention (mLife+points; points for provision and receipt of social support) produces significantly more weight loss at 12 months than the mLife without points (mLife) among 240 adults with overweight or obesity and  $\geq 3$  T2DM risk factors.

Hypothesis aim 1: The mLife+points group will lose more weight than the mLife group.

**Aim 2:** Examine the differences in social support provision and receipt

between groups at 12 months.

Hypothesis aim 2: That the mLife+points group will have greater levels of social support provision and receipt (both perceived and received) than the mLife.

## **Secondary Aims**

Examine usage patterns over time (e.g., do points sustain engagement and promote weight loss maintenance?), potential mediators (e.g., engagement/self-monitoring) and moderators (demographic factors such as sex, race, age), the usability and acceptability of the interventions and the association of social support provision/receipt and psychosocial factors (e.g., motivation, enjoyment) with weight loss. Create and test predictive models that can be applied to future grant applications.

## **Overview of Intervention**

This is a one-year remote intervention, randomized trial that will be conducted in two cohorts. Participants will be randomized to one of two groups: 1) mLIFE+points (n=120) or 2) mLIFE (n=120). Both groups will receive the same intervention, but in order to isolate the impact of points/social gaming, the mLIFE+points group will receive points for engaging in social support-related behaviors and the mLIFE will not.

All participants will be asked to track all their meals daily via the mLIFE App, use a Fitbit to track their physical activity, and use a Fitbit scale to track their body weight. Also, all participants will receive twice weekly podcasts and daily in-app tip of the day (based on Social Cognitive Theory and modeled from the Diabetes Prevention Program). The mLIFE App will also encourage and facilitate social support among participants. The intervention will last 12 months.

## **Overview of assessments**

Potential participants will be directed to a study website to learn more about the study and complete a screening questionnaire. If they qualify, they'll be invited to an orientation session where they'll learn more and sign a consent form. Participants will then complete online surveys measuring psychosocial variables and diet, and anthropometric data will be collected. Those who complete all baseline assessments will be randomly assigned to either the mLIFE+points or mLIFE group using a computer program allocation sequence, stratified by sex and baseline BMI (to ensure equal distribution of sex and weight classes among the two groups). All participants will complete assessments at baseline, 6, and 12 months. The study will involve two cohorts, each with 120 participants, staggered by 12 months.

# Trial registration

The study was pre-registered on [http://ClinicalTrials.gov \(NCT05176847\)](http://ClinicalTrials.gov (NCT05176847)) by [name] (PI), Project coordinator ([name]) has access to the study dashboard as well.

## IRB Review and Approvals

This study was initially approved by the University of South Carolina IRB on April 26th, 2021 (Pro00109784).

## Methods and Procedures

### Recruitment and Enrollment Plan

#### Population

The objective is to enroll a total of 240 participants (120 participants in Cohort 1 and 120 participants in Cohort 2). Recruitment for Cohort 1 commenced in February 2022, while recruitment for Cohort 2 commenced in February 2023.

---

#### Inclusion criteria

Assessed through an online screening survey and/or a telephone screening conversation.

- Be between the ages of 18-65 years
- Have a Body Mass Index between 25- 49.9 kg/m^2
- Have at least 3 risk factors for type 2 diabetes identified by the NIDDK
- Have an Android or iPhone and up-to-date mobile data plan
- Not being pregnant or planning on becoming pregnant during the study, or breastfeeding
- Not participating in another weight loss program
- Be free of major health or psychiatric diseases, drug or alcohol dependency.

---

#### Exclusion Criteria

Assessed through an online screening survey and/or a telephone screening conversation.

- Women that are pregnant, have been pregnant in the last 6 months, anticipate becoming pregnant in the next 24 months, or currently breastfeeding. Women who are pregnant should not be pursuing weight loss and should be under the direct care of a physician. Therefore, women who are pregnant or

who are anticipating they might be pregnant should not participate in this study. If a woman becomes pregnant during the study, she will be advised to consult her care provider and will be dropped from the study.

- Someone with an eating disorder (which will be screened with the Eating disorder Screen for Primary care [ESP]). If a participant has an eating disorder, they will be given the NIH brochure with information about eating disorders and contacts for help.
- Currently participating in a weight loss program or taking weight loss medications. Participants can be included in the study if they are trying to lose weight on their own, without any medication.
- Individual recently lost a significant amount of weight (>10lbs in the last 6 months).
- Current use of medications that may significantly impact blood glucose (i.e. metformin, steroids)
- Diagnosed with diabetes
- FOR SECOND COHORT: Currently taking any of long term weight loss medications, including Bupropion-naltrexone (Contrave); Liraglutide (Saxenda); Orlistat (Xenical, Alli); Phentermine-topiramate (Qsymia); Semaglutide (Wegovy); Setmelanotide (Imcivree).

---

## Recruitment Strategies

Participants were recruited nationwide, primarily via social media (Facebook and Instagram), television interviews, researchmatch.org, promotional materials (i.e., fliers and brochures), in- person targeted community outreach efforts (i.e. neighborhoods, churches, libraries, employers, recreation commissions, and coalitions). The recruitment process for the cohort 1 was launched on February 2022, and on February 2023 for the cohort 2. A waiting list was kept up to date during the intervention delivery of cohort 1.

All advertising strategies included a brief description of the study with an invitation to inquire for more details. Those inquiring will be directed to the study website: [www.mlifestudy.org](http://www.mlifestudy.org). All potential participants will be prompted to complete the online eligibility screening administered via RedCap, using the public link of the online survey.

---

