## Training Meeting Agenda & Notes for Study Personnel

1. Only participants who have completed ALL components of the assessment are confirmed to attend the training meeting.
2. Training meetings are conducted LIVE; the recording of screenshots and in-app tasks are used to conduct and time the meeting.
3. The Principal Investigator opens up the session with a welcome back message and introduces the mLife team.
4. Demo (live + screenshots) of activation of mLife account and link of Fitbit - participants to complete a task in-app (15 min).
5. Q/A in breakout rooms. A staff member will be assigned to each group. At this point, participants will be allowed to share their screen.
6. Demo of intervention components (live + screenshots of mLife app with comments related to the explanations) - include explanations of the graphs for self-monitoring (PA, BW, and Kcals), emphasis on the definitions and importance of each.
7. Demo of diet logging (tutorial video). Participants complete one item/meal log. Reminder set as a text message at 8 p.m. (participants' time zone) (10 min)
8. Demo of tips of the day and podcasts access (live + screenshots). Participants "read" the available tip of the day. The first podcast should be available for them to listen to and mark as listened.
9. Demo of Social support activities (tutorial video). Demo of outreach message. Participants write their first request for support and/or rate a response. They like someone's PA, diet logging, or BW. For the control group, review the checklist. For the +Points group, review the points system and leaderboard, emphasizing its importance in weight loss.
10. Q/A in breakout rooms. A staff member will be assigned to each group. At this point, participants will be allowed to share their screen.
11. Key items and dates. A journey

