## Dietary recalls

Dietary intake data (24-hour recalls) were collected and analyzed using the Automated SelfAdministered 24-hour (ASA24) Dietary Assessment Tool, version 2020 for cohort 1 and 2022 for cohort 2. Three unannounced dietary recalls were collected at each time-point. Invalid recalls (under 500kcals) were considered and participants were asked to complete another attempt. Total kcals for all valid recalls were averaged. A total of 5 weekdays and 5 weekend days are scheduled are each timepoints, thus enough makeup days are available for the

completion of the assessment.

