### ***Steps to request a dietary recall***

1. Before the first recall date, the number of recalls completed and remaining per participant has to be determined. Data is exported from ASA24 research site “tracking feature”. If a participant has not enough recalls remaining (8 remaining at 6-mo assessment and 4 remaining at 12- mo assessment), a new account must be assigned by highlighting the participant in the ac- counts Excel database located in OneDrive/mLife/Assessment Materials/Cohort/Dietary re- calls and pasting their identifying information on the last account available.
2. Active participants in each cohort are identified at each assessment time-point (baseline and 12 weeks) by generating the “consort report” from RedCap. Desired participants are enrolled study participants, with a participant status “active” and who haven’t completed the required dietary recalls for that time-point.
3. All databases generated for tracking each recall are securely stored in an Assessment Materials OneDrive folder per cohort. A folder within the Dietary Recalls section is labeled with the date of each recall.
4. On the scheduled day, a recall request is emailed to the participant in the morning using Out- look mail merge, which pulls participant information from the active participants spreadsheet.
5. In the early afternoon of the recall date, a research assistant would examine the completion of the day using the ASA24 Researcher Site. They would then create a list of people to remind to complete the day’s recall on Excel utilizing the earlier created spreadsheet of participants who were contacted that day to complete a recall. The research assistant would then conduct re- minder phone calls using Google Voice. If not able to be reached by phone call, participants are texted. These contacts would be noted in the Reminder Call Excel Spreadsheet. After completing these phone calls, the research assistant would contact the faculty members asso- ciated with the recalls for the assessment time-point and update them on their contacts. The phone call and text message scripts are below.
6. Participants are required to complete the recall before midnight Eastern time zone on the day that the recall was requested in order to be considered completed and valid. In addition, each participant’s recall had a threshold of 500 kcal to be considered valid.

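### Dietary recalls must be finished before midnight Eastern although recruitment is nationwide, so a complete recall finished late on the same local day further west does not count as valid

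*Combined protocol and SAP*

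**What the plan says.** The rule is in step 6 of the section on steps to request a dietary recall: "Participants are required to complete the recall before midnight Eastern time zone on the day that the recall was requested". The same sentence makes this a condition for the recall to count as completed and valid. A 500 kcal minimum is the only other validity condition given there. No local-time exception appears anywhere.

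Recruitment Strategies gives the catchment: "Participants were recruited nationwide, primarily via social media (Facebook and Instagram".

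The surrounding procedure is as follows.

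- Dietary recalls section: "Three unannounced dietary recalls were collected at each time-point". Energy intake is averaged over the valid recalls, and five weekdays plus five weekend days are scheduled at each time point to leave room for make-up attempts. The Assessments table specifies two weekday recalls and one weekend recall.
- Step 4: "On the scheduled day, a recall request is emailed to the participant in the morning".
- Step 5: "In the early afternoon of the recall date, a research assistant would examine the completion of the day using the ASA24 Researcher Site". Those who have not finished are phoned, then texted.
- Step 2: active participants who are still short of their recalls stay on the request list.
- Step 7: energy intake and recall date are imported to RedCap the following day.

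Elsewhere the study does use local time. The training meeting agenda describes the app diet-logging prompt: "Reminder set as a text message at 8 p.m. (participants' time zone".

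**The concern.** A validity rule should remove recalls that are unusable. The 500 kcal threshold does that. The Eastern deadline does something different for anyone living west of the Eastern zone: it can remove a complete, plausible recall made on the requested day, because of where the participant lives. The documents give no measurement reason for tying validity to Eastern time.

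Two things are at stake. First, usable dietary data are set aside, and the missingness becomes related to geography for an administrative reason. The recalls describe intake at baseline, 6 and 12 months, and the Adherence section relies on them. Second, participants bear a burden: a rejected recall has to be repeated on another day. At 6 and 12 months, $15 of the $50 incentive also depends on the recall component.

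**Working it through.** The plan states no figure on this point, so there is nothing of its own to reproduce. The check has two parts.

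**1. What the deadline means locally.** Inputs: the Eastern deadline (step 6), nationwide recruitment (Recruitment Strategies) and the standard US time-zone offsets, which are not in the documents. Local deadline = midnight minus the hours behind Eastern. The time affected is the interval from that deadline to local midnight.

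| Zone | Hours behind Eastern | Local deadline | Same-day hours affected |
|---|---|---|---|
| Central | 1 | 11 p.m. | 1 |
| Mountain | 2 | 10 p.m. | 2 |
| Pacific | 3 | 9 p.m. | 3 |
| Alaska | 4 | 8 p.m. | 4 |
| Hawaii | 5 (winter) or 6 (summer) | 7 p.m. or 6 p.m. | 5 or 6 |

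Only recalls finished inside that interval are affected. One finished at 9:30 p.m. Pacific fails. One finished at 8:30 p.m. Pacific passes.

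**2. How far the make-up days absorb the loss.** Inputs: two weekday recalls and one weekend recall needed (Assessments table); five days of each type scheduled (Dietary recalls). Let p be the chance that a request yields a valid recall. The documents give no value for p, so it is an assumption and is ranged. Independence between days is also assumed.

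P(full set) = P(at least 2 of 5 weekdays) × P(at least 1 of 5 weekend days) = [1 − (1−p)^5 − 5p(1−p)^4] × [1 − (1−p)^5]

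- p = 0.9: 0.99954 × 0.99999 = 0.9995
- p = 0.8: 0.99328 × 0.99968 = 0.993
- p = 0.7: 0.96922 × 0.99757 = 0.967
- p = 0.6: 0.91296 × 0.98976 = 0.904
- p = 0.5: 0.81250 × 0.96875 = 0.787

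Suppose, purely for illustration, that the Eastern deadline lowers p by 0.10 for a participant who tends to finish late. The chance of a full set then falls by:

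- 0.9 to 0.8: 99.95% − 99.3% = about 0.7 percentage points
- 0.7 to 0.6: 96.7% − 90.4% = 6.3 points
- 0.6 to 0.5: 90.4% − 78.7% = 11.7 points

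So the consequence is negligible where daily completion is high and noticeable only where it is already poor. A trial-level figure would also need the share of participants in each zone and the times at which recalls were finished. Neither is in the documents, so the number of recalls lost, or recovered by a change, cannot be computed.

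**The case against.** The strongest defence is that the procedure already leaves ample room. The request arrives in the morning, staff follow up the same day, there are ten scheduled days for three recalls, and anyone still short is asked again. The guidelines for interacting with participants also ask that deadlines be communicated in advance and more than once, so a Pacific participant can be told to finish by 9 p.m. A single central deadline is simple for staff who import the data next day. All of this stands, and it is why the effect is likely to be small. It does not supply a reason to reject a recall that is complete, above the threshold and made on the right local day. If the early-afternoon check runs on Eastern time, which the text does not say, it also falls three hours earlier in a Pacific participant's day.

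The 8 p.m. local-time text is weak support for calling the plan inconsistent. It is a prompt for app diet logging, an intervention component, and the recalls are an assessment. It shows only that the study can work in local time.

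Three stronger readings are tempting, and the documents do not support them.

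- A reader might infer that western participants' same-day recalls are discarded as a class. Only those finished between midnight Eastern and local midnight are affected.
- A reader might infer that fewer western participants reach three recalls. That is possible in direction, but no completion times or regional counts are given, and the make-up days may absorb it entirely.
- A reader might infer that the deadline keeps randomised participants out of the intervention, because "Only participants who have completed ALL components of the assessment are confirmed to attend the training meeting". That would require someone to fall short across ten scheduled days because of late-evening completion. The gap between randomising at 50% of baseline assessments and requiring all of them for training exists in every time zone, and is a separate matter.

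**Conclusion.** The point holds in a narrow form. Under step 6, a complete recall above 500 kcal that is finished after 11 p.m. Central, 10 p.m. Mountain or 9 p.m. Pacific on the requested day (earlier in Alaska and Hawaii) is treated as not valid, and must be repeated or is lost. This follows directly from the text and needs no assumption beyond the standard time-zone offsets.

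Its size is unknown and probably small. The percentages above rest on assumed completion rates and describe an affected individual, not the trial. The deadline is identical in both arms, so no between-arm difference is expected from it. The recalls are listed among potential drivers of weight loss and serve as a dietary and adherence measure. They are not the Aim 1 outcome (weight) or an Aim 2 outcome (social support), so neither primary comparison is threatened. This is a minor, inexpensive improvement.

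**What to change.** In step 6 of the dietary recall procedure, replace the Eastern deadline with midnight in the participant's own time zone on the day of the request. Use the same cut-off when completion is checked for the RedCap import. Next-day import remains feasible: local midnight is 3 a.m. Eastern for a Pacific participant and at latest 6 a.m. Eastern for one in Hawaii.

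The Dietary recalls section describes collection in the past tense for both cohorts, so rewording alone may come too late. Where recalls have been collected and completion times are available, apply the local-time rule when deciding which recalls are valid for analysis. The import in step 7 is described as holding energy intake and date, so the clock time would have to come from another source, and the documents do not say whether one was kept. Because intake is averaged over all valid recalls, a reinstated recall can enter the mean alongside any repeat.

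The cost is one changed sentence and a time-zone field in the tracking sheet. For recalls already collected, there is also a single pass through those marked late.

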## Recruitment and Enrollment report

Recruitment and enrollment (as well as retention) will be reported weekly during the recruitment timeframe using Consolidated Standards of Reporting Trials guidelines. Weekly data will be pulled from the RedCap recruitment projects using the reports feature. The project manager will be responsible for tracking potential

participants who contact the study office via phone or email. This involves reviewing the weekly information registered in the screening report from RedCap. Key metrics to track include the number of contacts, referral sources (e.g., social media, community events), the number of individuals screened online and then by phone, the number of eligible participants, and the number of participants enrolled in the study.

## **Training Plan**

All staff working on participant recruitment and retention, assessment, and/or intervention are required to complete both Good Clinical Practices Training (available at: <https://www.sbm.org/training/good-clinical-practice-for-social-and-behavioral-research-elearning-course>), and Social and Behavioral Citi Training (available at: <https://about.citiprogram.org/en/course/human-subjects-research-2/>). Certificates for all personnel are uploaded to OneDrive/mLife Study/IRB/Citi training certificates, and kept up to date.

The project coordinator sets reminders to personnel who are required to complete the refresher and update their certification.

Any staff or students participating in the screening process must be trained by a Project coordinator. This training will include observation of phone screenings conducted by experienced staff and being observed by the Project Manager or experienced staff in conducting a phone screening.

All training was conducted online, and recordings were available as part of the personnel training and refreshers. Tutorial videos are listed in the document for each section of the current document.

